7.7.1. Study Intervention Exposure

The following will be summarized at each treatment visit by each of the 7 cohorts for each treatment area (left or right) using descriptive statistics:

- Total number of injections given
- Dose (mg) of each treatment visit
- Duration of exposure (refer to Table 17 for computation of exposure duration)

The number of participants treated at each treatment visit will be summarized using frequency and percentages by treatment area for each cohort.

A participant listing of intervention exposure information will be provided by cohort.

7.7.2. Adverse Events

All AE summary tables will include only TEAEs, unless otherwise specified. TEAEs will be summarized by SOC and PT. A participant will only be counted once per SOC and PT.

For TEAEs by severity grade (mild, moderate, severe), if a participant has multiple events occurring in the same SOC or same PT, then the event with the maximum intensity (ie, severe) will be counted

For TEAEs by relationship to study intervention, if a participant has multiple events occurring in the same SOC or same PT, the event with the highest association (ie, related) to study intervention will be summarized.

An overall summary of TEAEs and TEAEs related to study intervention will be presented and will include:

- Total number of TEAEs reported
- Total Number of TEAEs of Injection site reaction
- Total number of TEAEs reported by severity
- Participants with any TEAE
- Participants with TEAEs of Injection site reaction
- Participants with any serious TEAE

- Participants with any severe TEAE
- Participants with no severe TEAEs, but at least one moderate TEAE
- Participants with no severe TEAEs, but at least one mild TEAE
- Participants with any TEAEs leading to intervention interruption/discontinuation
- Participants with any TEAEs leading to withdrawal from study
- Participants with any TEAEs resulting in death

The following summary tables will be presented by SOC and PT:

- All TEAEs
- Study intervention related TEAEs
- TEAEs by severity
- Study intervention related TEAEs by severity
- Duration of study intervention related TEAEs
- Serious TEAEs

Refer to Table 17 for computation of duration of AEs. All TEAEs will be presented for Left Buttock, Right Buttock, Others (Not Applicable) and overall. For AEs where treatment location is neither Left Buttock nor Right Buttock will be collected as "Not Applicable" and is displayed under Others (Not Applicable) category.

The proportion of participants reporting TEAEs of injection site reaction in the left vs the right buttock will be summarized using frequency, proportion and corresponding 95% CI based on the Clopper-Pearson method.

The most common non-serious TEAEs by order of frequency (most frequent, 2nd most frequent, and 3rd most frequent) will be summarized by PT. The most common non-serious AEs are those with any PT that at least 5% of the participants reported at least once.

The following listings will be presented by participant:

- All AEs
- Fatal AEs
- Non-fatal serious AEs
- Non-fatal non-serious AEs leading to study discontinuation
- Non-fatal non-serious AEs resulting in intervention interruption/withdrawn

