
For Cohort 7 the labeled dose, concentration and depth will be used throughout the study, however, there will be 2 sub-cohorts (7a and 7b) each with asynchronous treatment sessions of QWO (CCH-aaes) and different timing of treatment with oral tranexamic acid.

- For Cohort 7a, oral tranexamic acid will be provided by the sponsor and self-administered by participants, before and after the investigational buttock receives the first dose of QWO (CCH-aaes) on Day 1. The control buttock will receive the first treatment of QWO (CCH-aaes) on Day 22 to allow for the systemic effects of oral tranexamic acid to dissipate.
- For Cohort 7b, tranexamic acid will be provided by the sponsor and self-administered, orally, by participants, before and after the investigational buttock receives the first dose of QWO (CCH-aaes), on Day 22. This corresponds to the second dose of QWO (CCH-aaes) for the control buttock. This allows for a treatment session of the control buttock (initial treatment) without the presence of oral tranexamic acid.

Staggering administration of tranexamic acid with QWO (CCH-aaes) will allow for a comparison between the investigational and control buttocks within a cohort and between cohorts.

• See Section 3.3.6 for the rationale for administration of tranexamic acid.

The endpoints will evaluate the proportion of participants with a reduction (improvement) in bruising severity on the variable buttock receiving study intervention vs the control side, as reported by the investigator.

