5.3. Justification for Endpoints

The primary endpoint, for Cohorts 1 to 6, will be the investigator's assessment of bruising in each buttock based on observed, in-person assessments on the IABSS, at Visit 3, three to five days after the initial QWO (CCH-aaes) injection. This endpoint will be assessed after the first treatment visit since this is historically when bruising has been the most severe. For Cohorts 1-6 this will occur at Visit 3.

The primary endpoint for Cohort 7a is the proportion of participants whose left buttock (investigational side), at Visit 3, demonstrates at least 1-level lower score versus the right buttock (control side), at Visit 8 on the IABSS. The primary endpoint for Cohort 7b is the proportion of participants whose left buttock (investigational side), at Visit 8, demonstrates at least 1-level lower score versus the right buttock (control side), at Visit 3, on the IABSS. These visits are three to 5 days after initial QWO (CCH-aaes) injection for each respective buttock.

For Cohorts 7a and 7b, similar to Cohorts 1 to 6, this endpoint will be assessed after the first treatment visit since this is historically when bruising is most severe. In Cohorts 1 to 6, for all endpoints and in Cohorts 7a and 7b, for all endpoints other than the primary endpoint, all participants enrolled in the study will serve as their own control, since the study is designed to evaluate the effect of using different doses, different concentrations, and different methods of injection for QWO (CCH-aaes) applied unilaterally to the investigational side. The bruising on the left-buttock (investigational side) will be compared to the right buttock (control side).

The comparison of buttocks for the primary endpoint by visit for Cohorts 7a and 7b is shown in Figure 1.

Figure 1: Primary Endpoints for Cohorts 7a and 7b

Cohort 7a				
	Control Side	Investigational Side		
Day -1		TXA (Study Days -1,1,2,3,4)		
Day 1	-	QWO Dose 1		
Day 21				
Day 22	QWO Dose 1	QWO Dose 2		
Day 43	QWO Dose 2	QWO Dose 3		
Day 64	QWO Dose 3	-		

Cohort 7b				
	Control Side	Investigational Side		
Day -1				
Day 1	QWO Dose 1	-		
Day 21		TXA (Study Days 21,22,23,24,25)		
Day 22	QWO Dose 2	QWO Dose 1		
Day 43	QWO Dose 3	QWO Dose 2		
Day 64	-	QWO Dose 3		

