	• Cohorts 7a and 7b: The proportion of participants within each cohort (ie, 7a and 7b) whose left buttock (investigational side) demonstrates at least 1-level lower score versus the right buttock (control side), on the IABSS, by corresponding treatment visit by buttock (first dose of QWO [CCH-aaes] on the investigational buttock with tranexamic acid vs the first dose of QWO [CCH-aaes] without tranexamic acid on the control side; second dose of QWO [CCH-aaes] on the investigational buttock vs second dose of QWO [CCH-aaes] on the control side; third dose of QWO [CCH-aaes] on the investigational side vs third dose of QWO [CCH-aaes] on the control side); and at each follow up visit thereafter.
To assess the level of aesthetic improvement of cellulite after treatment with QWO (CCH-aaes).	• The proportion of participants with an improved (+1 or better) score on the Investigator-Global Aesthetic Improvement Scale (I-GAIS) by treatment area at Days 22, 43, 64, 90, 135 and 180 Visits. The I-GAIS is a 7-point scale ranging from +3 (very much improved) to -3 (very much worse).
To assess the safety of QWO (CCH-aaes) for each study intervention in participants with cellulite.	• Proportion of participants reporting each treatment-emergent adverse events (TEAEs) throughout the study.
To assess the safety of QWO (CCH-aaes) for each study intervention in participants with cellulite.	• Proportion of participants reporting TEAEs of injection site reactions in the left buttock (investigational side) vs the right buttock (control side).
Exploratory	

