43 with the control side treated with QWO (CCH- aaes) on Days 22, 43 and 64. Participants in Cohort 7b will have the investigational side treated on Days 22, 43, and 64 and the control side treated on Days 1, 22, and 43. Tranexamic acid will be provided by the site and self-administered by all participants enrolled in Cohort 7. Participants in Cohort 7a will take tranexamic acid 1300 mg orally TID for 5 days (prior to the day of the first injection of QWO (CCH-aaes) of the investigational buttock (Day -1), the day of the first injection (Day 1), and for the 3 days following the first injection (Days 2 to 4). Participants in Cohort 7b will take tranexamic acid orally TID for 5 days (prior to the day of the second injection on Day 21, the day of the second injection (Day 22) and for the 3 days following the second injection (Day 23 to Day 25).

There will be 4 follow-up visits (1 to 2 days, 3 to 5 days, 6 to 9 days and 10 to 14 days) after each treatment (Cohort 6 will have a fifth follow-up visit at 18-24 days after initial treatment visit). The effect of the different QWO (CCH-aaes) doses, strengths (concentrations), diluent additives, depths of injection, and methods of injection on the severity of bruising will be assessed by the investigator using the IABSS. To assess the effect of QWO (CCH-aaes) on the severity of cellulite (efficacy), the investigator will complete the I-GAIS. Each buttock will be evaluated independently.

After the completion of the treatment period, there will be 3 follow-up visits at Day 90, 135 and 180/End of Study (EOS)/Early Termination (ET).

For more details, refer to protocol section 5.1.

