6.2. Derived Variables

Table 17 defines the derived variables for study parameters.

Table 17: Derived Variables and Definition

Variable	Definition			
Age Group (years)	18 - <30 30 - <45 45 - 60			
Height (cm)	If height is recorded in inches, then height is equal to the recorded value multiplied by 2.54 and then rounded to 1 decimal place.			
Weight (kg)	If weight is recorded in pounds, then weight is equal to the recorded value multiplied by 0.454 and then rounded to 1 decimal place.			
Body Mass Index (BMI)	BMI will be computed using height measured at screening and body weight measured at respective visits as, BMI (kg/m^2) = Weight (kg) / Height $(m)^2$			
Relative Day	The day of first injection of study intervention will be considered as relative Day 1.			
Study Day (for assessment on or after Day 1)	Study Day will be computed as: Date of Assessment – Date of Day 1 + 1			
Study Day (for assessment before Day 1)	Study Day will be computed as: Date of Assessment – Date of Day 1			
Baseline	Baseline is defined as the last non-missing measurement/assessment prior to the first dose of study intervention. The assessments made in unscheduled visits will be considered in calculation of the baseline.			
Baseline for Vital Signs on Injection Days	For vital signs on injection days, the baseline value will be the vital sign measure immediately prior to the first dose of study intervention.			
Change from baseline	Change from baseline will be derived as: post baseline visit/time point value – the baseline value.			
Last (analysis)	Last is defined as the last non-missing measurement/assessment post the first dose of study drug intervention			
Duration (Minutes) of Exposure at each visit	Date/Time of Last Injection – Date/Time of First Injection			
Duration (Days) of AE	AE end date – AE start date + 1			
AE Start Day	AE start date – Date of Day 1 + 1			
AE Stop Day	AE end date – Date of Day 1 + 1			
Cellulite History (years) (≥ 5 or ≤ 5)	Day of Screening – Start Date of Cellulite History			

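### In Cohort 7 the whole-study left-versus-right comparison of injection-site TEAEs does not isolate tranexamic acid; the mild row of the TEAE overview also overlaps the moderate row, and one vital-sign baseline needs clarifying

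*SAP*

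**What the plan says.** **Injection-site TEAEs.** SAP Table 1 lists a secondary safety endpoint comparing the left (investigational) with the right (control) buttock on injection-site TEAEs, with no time window. SAP 7.7.2 carries it into the analysis: "The proportion of participants reporting TEAEs of injection site reaction in the left vs the right buttock will be summarized using frequency, proportion", with a Clopper-Pearson 95% interval. Neither place treats Cohort 7 differently from the other cohorts.

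For Cohort 7b, SAP 3.1 has "the investigational side treated on Days 22, 43, and 64 and the control side treated on Days 1, 22, and 43". Tranexamic acid is taken on Days 21 to 25. Protocol 5.2 says of the Day 22 session: "This corresponds to the second dose of QWO (CCH-aaes) for the control buttock". The same section delays the first control injection in 7a so that the drug's systemic effects can dissipate.

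**Severity rows.** The overall TEAE summary in SAP 7.7.2 has a row for any severe TEAE, a row for no severe but at least one moderate, and then "Participants with no severe TEAEs, but at least one mild TEAE". The tables by SOC and PT instead count each participant once, at maximum intensity.

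**Injection-day vital signs.** SAP Table 17 says that, for injection days, "the baseline value will be the vital sign measure immediately prior to the first dose of study intervention". SAP 7.7.4 uses the Day 1 value for the by-visit analyses. SAP 3.16.1 collects a pre-injection value at every treatment visit.

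**The concern.** In Cohorts 1 to 6 the left buttock receives the study intervention at every session, so a whole-study left-versus-right count compares intervention with control. Cohort 7 is different: the intervention is a short systemic course tied to one session, and in 7b the control side is also injected during that course. A table labelled investigational versus control would suggest a comparison of injections with and without tranexamic acid. In 7b it is not one, and a small difference could be misread as evidence that the drug does little for injection-site reactions.

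The SAP recognises this staggering elsewhere. The Cohort 7 IABSS endpoints are matched by dose number (7.6.1.2, 7.6.1.3, 7.6.2.2), and I-GAIS at Day 22 is limited to the buttock already treated (3.8.3). The injection-site endpoint received no such adjustment.

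The denominator is also unsettled. The Safety Population needs only one injection on either side (SAP Section 5). A 7a participant who leaves before Day 22 never has the right side injected; a 7b participant who leaves then never has the left side injected.

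The other two points are smaller. The severity overview will not reconcile with the maximum-intensity tables, and two programmers could code the injection-day baseline differently.

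**Working it through.** The documents give no event rate, power or expected difference for these outputs, so there is no planned figure to reproduce.

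**1. Sessions under tranexamic acid.** Injection days are from SAP 3.1; drug days are from SAP 3.1 and Protocol 5.3, Figure 1.

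| Cohort and side | Dose 1 | Dose 2 | Dose 3 | Sessions on drug |
|---|---|---|---|---|
| 7a left | Day 1, on drug | Day 22 | Day 43 | 1 of 3 |
| 7a right | Day 22 | Day 43 | Day 64 | 0 of 3 |
| 7b left | Day 22, on drug | Day 43 | Day 64 | 1 of 3 |
| 7b right | Day 1 | Day 22, on drug | Day 43 | 1 of 3 |

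By dose number, 7b has a contrast at dose 1 (left with drug, right without), the reverse at dose 2, and none at dose 3. Pooling sessions sets the first two against each other.

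**2. What the pooled comparison can show.** Assume per-dose event probabilities p1, p2, p3 without drug, a risk ratio r in a covered session, and independent sessions. For the proportion with any event over the study:

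- 7b, left minus right = −(1−p3)(1−r)(p1−p2)
- 7a, left minus right = −p1(1−p2)(1−p3)(1−r)
- dose 1 only, left minus right = −p1(1−r)

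At r = 0.5, in percentage points:

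| p1 / p2 / p3 (assumed) | 7b pooled | 7a pooled | Dose 1 only |
|---|---|---|---|
| 0.50 / 0.50 / 0.50 | 0 | −6.2 | −25 |
| 0.84 / 0.70 / 0.60 | −2.8 | −5.0 | −42 |
| 0.84 / 0.50 / 0.40 | −10.2 | −12.6 | −42 |
| 0.84 / 0.30 / 0.20 | −21.6 | −23.5 | −42 |

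For example, the second row in 7b is 0.40 × 0.5 × 0.14 = 0.028. At r = 0.75 the entries halve, because 1−r does. The 7b result contains the factor p1−p2: it depends on how much worse dose 1 is than dose 2 as well as on the drug.

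**3. Severity rows.** There are 8 presence-or-absence patterns of severe, moderate and mild events, 7 of them with at least one TEAE. Under the current rows, the pattern moderate and mild without severe enters two rows; the other six enter one. Invented example: 3 participants with a severe event, 8 with moderate as maximum (6 of whom also have a mild event) and 3 with mild only. The rows read 3, 8 and 6 + 3 = 9, summing to 20 for 14 participants. If the mild row also excludes moderate events, each of the 7 patterns falls in exactly one row.

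**4. Vital-sign reference.** A low systolic flag needs 90 mmHg or less and a fall of at least 20 mmHg from baseline (SAP Table 15). Invented readings at a later session:

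- Day 1 value 118, same-day pre-injection 100, post-injection 90: a fall of 28 from Day 1 (flagged), but 10 from the same day (not flagged).
- Day 1 value 105, same-day pre-injection 115, post-injection 90: a fall of 15 from Day 1 (not flagged), but 25 from the same day (flagged).

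The choice of baseline can change the flag in either direction.

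**The case against.** The strongest reply is that this table is not the estimate of the tranexamic acid effect. Its objective is safety, it is descriptive with no test named, and the effect on bruising is analysed dose-matched in the primary and secondary IABSS endpoints. All AEs are listed and an AE start day is derived, so timing can be recovered. That stands and limits the consequence, but it does not correct a table whose side labels imply a contrast that 7b lacks. The dilution in 7a does follow from the design, and 7a keeps a one-sided contrast.

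A reader might infer that no drug effect could appear at all in 7b. The documents do not support that. Protocol 5.2 says bruising is most robust after the first treatment, and the drug covers dose 1 on the left but dose 2 on the right, so a diluted difference can remain. It is exactly zero in the model above only if the first two doses carry equal rates. A reader might also argue from the 84% bruising rate in Protocol 3.3.1 that both sides are near a ceiling. That figure is per subject from earlier use, not per side or per cohort.

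On severity, the SAP never says the overview rows should add up, and the label is literally true. But the preceding row excludes the more severe category, and this one does not follow that pattern.

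On vital signs, a reader might conclude that the output is wrong and put a rate on false flags. A separate injection-day row, with Day 1 tied to the by-visit analyses, suggests that a per-visit baseline may have been intended. The documents give no blood-pressure variability, and a flag needs both the level and the change, so no error rate can be stated. SAP Module 2 shells, not available here, might settle this or the severity rows.

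**Conclusion.** The main point holds. In Cohort 7 the pooled injection-site comparison does not isolate tranexamic acid: exposure is one session of three on each side in 7b, and one against none in 7a. This follows from the schedule alone. The size of the dilution rests on assumed rates, a risk ratio of 0.5 and independent sessions: a 42-point difference at dose 1 becomes 2.8 to 21.6 points in 7b and 5.0 to 23.5 in 7a. The values are illustrative, but the mixing of drug and dose number in 7b is not.

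The severity-row overlap is a matter of logic, confined to the moderate and mild rows of one overview. The vital-sign item is a minor ambiguity to clarify, not a demonstrated error. None of the three affects the primary endpoint.

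**What to change.** 1. For Cohorts 7a and 7b, add a dose-aligned table of injection-site TEAEs by side. Count events with onset from that side's first QWO injection until the participant's actual next treatment session or, if there is none, until the end of an equal-length window. Use participants injected on that side as the denominator. Keep the whole-study table. Fixed calendar windows would not do: treatment visits on Days 22 and 43 may each move by 3 days, so the second interval can run from 40 − 25 = 15 to 46 − 19 = 27 days.
2. Reword the third severity row as no severe or moderate TEAEs, but at least one mild TEAE.
3. In Table 17, state that the injection-day baseline is the pre-injection value of the same treatment day, and keep Day 1 for the by-visit analyses.

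The cost is SAP wording and one extra table. Onset date, AE location and same-day pre-injection vital signs are already collected. The downside is fewer events in the Cohort 7 window, with only 15 participants planned in each of 7a and 7b. The two sides are also still compared in different calendar periods, as they already are for IABSS.

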7.7.3. Clinical Laboratory

Hematology and biochemistry results will be summarized by treatment area and overall using descriptive statistics for observed and change from baseline to Last.

The PCI laboratory values will be summarized by treatment area and overall using frequency and percentages. Refer to Table 14 for PCI criteria.

A participant listing (including urinalysis results) will be presented for all laboratory parameters. Serum and urine pregnancy test results will also be listed.

7.7.4. Vital Signs

Vital signs (systolic and diastolic blood pressure, pulse rate, body weight, BMI and body temperature) will be summarized by each cohort and overall using descriptive statistics for the observed and change from baseline values for all assessments visits. Baseline (study baseline) will be the vital sign value taken at Day 1, 2 hours prior to injection for the by-visit analyses.

The PCI vital signs values will be summarized by each cohort and overall using frequency and percentages. Refer to Table 15 for PCI criteria.

A participant listing will be presented for vital sign results.

7.7.5. Physical Examination

Physical examination results (by body system) at baseline will be presented by cohort and overall using frequency and percentages.

A participant listing will be presented for the physical examination result (by body system).

8. CHANGE FROM PROTOCOL

This SAP is prepared based on Protocol Amendment 2: August 12, 2022. Table 18 lists any significant changes in the SAP from what is proposed in the protocol.

Table 18: Changes from Protocol

Text in Protocol	Change in SAP	Justification
Section 9.1.3 - The investigator (or qualified designated physician) will determine the Fitzpatrick skin type for all participants on Day 1.	Section 3.9.3 - The investigator (or qualified designated physician) will determine the Fitzpatrick skin type for all participants on Screening.	As per SoA (Table 3, Table 4, Table 5, and Table 6) Fitzpatrick skin type for all participants should be on Screening.
Section 7.5: The start and stop date, dose, unit, frequency, route of administration, and indication for all prior medications (taken within the 90 days prior to the Screening Visit) will be recorded.	Any medication/procedure taken/done prior to first injection (Day 1) will be reported as prior medication/procedure.	As per discussion with Endo, this has been updated.
Section 7.1: In Table 2, the footnotes are incorrectly aligned with the table text.	SAP Section 3.5: In Table 7, footnotes are now correctly aligned with table text.	
For example, in the text:	For example, in the text:	
Cohort 7a	Cohort 7a	
Right Buttock (control side) ^a	Right Buttock (control side) ^b	
where,	where,	
^a The investigational side will be treated with QWO (CCH-aaes) on Days 1, 22, and 43.	b The control side will be treated with QWO (CCH-aaes) on Days 22, 43, and 64.	

9. **REFERENCES**

- 1. Protocol Amendment 2: APHRODITE-1: A Phase 2, Open Label, Self-Controlled Study of Different Interventions to Reduce Bruising Following CCH-Aaes Treatment for Cellulite of the Buttocks in Adult Females [Clinical Study Protocol EN3835-226 CEL]. Dated: August 12, 2022
- 4. Protocol Administrative Change Letter No. 01: APHRODITE-1: A Phase 2, Open-label, Self-controlled Study of Different Interventions to Reduce Bruising Following CCH-aaes Treatment for Cellulite of the Buttocks in Adult Females [Clinical Study Protocol EN3835-226 CEL]. Dated: September 15, 2022

